5.3 Treatment Assignment and Blinding

This is an open-label, sequential enrollment study; therefore, no randomization or blinding procedures will be performed.

5.4 Replacement of Patients

Patients who are lost to follow up or withdraw consent for study participation prior to receiving HBI-8000 or who withdraw in Cycle 1 for reasons unrelated to drug toxicity or PD will be replaced.

5.5 Populations for Analysis

5.5.1 Safety Population

The safety analyses population will include all patients who receive at least one dose of HBI-8000. The safety analyses population will be the primary population for evaluating treatment administration / compliance and safety in the study.

5.5.2 Efficacy Population

Efficacy should be analyzed using FAS and PPS.

The FAS is defined as Patients meeting all eligibility criteria and having received at least one dose of study medication, and at least one efficacy assessment of disease with either imaging studies or clinical examination after receiving study medication.

The PPS is defined as Patients meeting all eligibility criteria and having completed Cycle 1 treatment or discontinued study treatment during cycle 1 due to clinical PD. It should be noted that the PPS includes subjects who discontinue within Cycle 1 due to clinical PD without imaging studies to assess disease status.

In addition, Patients who are assessed as Non-PTCL by the central pathology review committee should be excluded from the FAS and PPS for efficacy. The non-PTCL subjects will be included in safety analysis for the study.

The primary efficacy analysis is conducted in the PPS. The Efficacy analysis using the FAS will be also reported.

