Disease diagnosis including histological subtypes will be confirmed by central pathology review conducted by independent pathologists.	
Efficacy should be analyzed using Full analysis set (FAS) and Per protocol set (PPS). The FAS is defined as Patients meeting all eligibility criteria and having received at least one dose of study medication, and at least one efficacy assessment of disease with either imaging studies or clinical examination after receiving study medication.	
The PPS is defined as Patients meeting all eligibility criteria and having completed Cycle 1 treatment or discontinued study treatment during cycle 1 due to clinical PD. It should be noted that the PPS includes subjects who discontinue within Cycle 1 due to clinical PD without imaging studies to assess disease status.	
In addition, Patients who are assessed as Non-PTCL by the central pathology review committee should be excluded from the FAS and PPS for efficacy. The non-PTCL subjects will be included in safety analysis for the study.	
The primary efficacy analysis is conducted in the PPS. The Efficacy analysis using the FAS will be also reported.	
It is estimated that 40 evaluable patients are adequate to provide efficacy assessment. Assuming a 30% ORR in this population of 40 evaluable patients, the conclusion would be that there is a 95% chance that the ORR in this protocol population would lie between 15.8% and 44.2%. The power for showing the response rate $>10\%$ at 5% two-sided alpha in 40 patients is 89%.	
All patients who have received any amount of study medication will be considered as evaluable for safety. Safety data will be summarized with descriptive statistics and frequency tables and will include AEs, hematology, coagulation, serum chemistry, urinalysis, vital signs, and ECG data. Laboratory values will be summarized by numerical value and toxicity grade.	

TABLE OF CONTENTS

SIGNATURES.....	2
HBI-8000-203 PROTOCOL SYNOPSIS	3
LIST OF ABBREVIATIONS AND DEFINITIONS OF TERMS	13
1.0 INTRODUCTION.....	15
1.1 Background Information	15
1.2 Histone Deacetylase as a Therapeutic Target in Cancer... 	15
1.3 Rationale for the Use of HBI-8000 for the Treatment of Cancer	16
1.3.1 Immunomodulatory Mechanisms Integrate with Cancer Cell Intrinsic Mechanisms of Cell Killing by HDACi.....	17
1.4 Nonclinical Studies.....	18
1.5 Clinical Pharmacology.....	19
1.5.1 Absorption	19
1.5.2 Distribution.....	20
1.5.3 Metabolism and Excretion.....	20
1.6 Clinical Studies.....	20

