2.6.3 Treatment Phase

All assessments must be performed as per the Schedule of Events (see Section 9.1). Assessments scheduled on the day of study treatment should be performed prior to taking study drug, unless otherwise noted in the schedule of assessments.

Assessment of tumor response will be scheduled by end of the eighth week, then every 8 weeks (\pm 1 week) from C1D1. However, if a patient develops clinical signs and symptoms of PD, or unacceptable toxicity occurs, tumor assessment may be performed sooner as needed. For the patients with skin lesions, decision on treatment discontinuation should be based on computed tomography (CT) or positron emission tomography (PET-CT) assessment, not Modified Severity Weighted Assessment Tool (mSWAT) scores. In other words, if imaging studies showing SD or PR while mSWAT score increases, treatment will continue.

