2.6.4 End of Treatment Safety Follow-up Visit

All patients receiving at least one dose of HBI-8000 and discontinuing treatment for any reason except death will be assessed 30 (\pm 3) days after the last dosing of study drug, before the initiation of new cancer treatment or before the initiation of administration of commercial product of HBI-8000, whichever is earlier. Any patient for whom study treatment has been discontinued should complete study procedures listed in the EoT visit. At EoT safety visit, evaluations will include physical examination, vital signs, body weight, ECOG performance

status, hematology, blood chemistry, urinalysis, pregnancy test (if applicable), ECG, and assessment of any ongoing adverse events. If a patient discontinues study treatment before PD is recorded, and if the last tumor assessment was >30 days earlier from the EoT visit, tumor assessment should be performed at EoT. In these patients, further tumor assessments are to be performed approximately every 3 months \pm 2 weeks until PD or the start of new cancer therapy whichever occurs first, unless consent to study participation is withdrawn or by completion of the whole study. If subjects cannot visit at site for this examination due to COVID-19 situation, investigators can skip the examination, and the assessment is to be performed approximately every 6 months \pm 2 weeks. In this case, the investigator should document that fact in the medical record.

Patients with HBI-8000-related AEs of Grade ≥ 2 observed at the EoT visit should be followed-up and assessed monthly (phone calls/clinic visits) until the AEs have resolved to Grade ≤ 1 or are determined to be chronic, or patient receives other anti-cancer therapy.

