2.6.6 Patient Withdrawal

Patients have the right to withdraw from the study at any time for any reason, and the investigator should try to ascertain the reason for withdrawal as completely as possible. The investigator also has the authority to determine whether a patient should be discontinued from the study. Study treatment may be discontinued and the patient withdrawn from the study under the following circumstances:

- Unacceptable toxicity (AE)
- Progression of the disease under study, except for isolated progression in skin lesion
- Decision by the investigator to permanently discontinue study drug administration
- Intercurrent illness that would, in the judgment of the investigator, affect clinical assessments, patient safety, or follow-up significantly
- Significant protocol deviations that jeopardize the usefulness of the data
- Repeated patient noncompliance
- Patient is beginning another anti-cancer treatment protocol
- Patient becomes pregnant
- Patient requests to withdraw informed consent
- Study termination by the sponsor

All patients who withdraw from study treatment must complete an EoT visit, to be performed 30 ± 3 days after the last dosing of the study drug (see Section 9.1), before the initiation of new cancer treatment or before the initiation of administration of commercial product of HBI-8000, whichever is earlier. A patient may withdraw consent for treatment but still allow follow-up, in which case he/she should be followed for safety, survival, and disease status. If a patient has withdrawn consent to study participation entirely, no subsequent follow-up will be performed.

Patients who are lost to follow up or withdraw consent for study participation prior to receiving HBI-8000 or who withdraw before completing Cycle 1 for reasons unrelated to drug AEs or PD will be replaced.

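### The primary ORR set leaves out Cycle 1 toxicity stops and some Cycle 1 deaths, which probably raises the ORR slightly; the FAS recovers most of them but not all

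*Combined protocol and SAP*

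**What the plan says.** Section 5.5.2 and the synopsis define two efficacy sets. Both require that all eligibility criteria are met, and both drop patients found to be non-PTCL on central pathology review.

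- **PPS:** patients "having completed Cycle 1 treatment or discontinued study treatment during cycle 1 due to clinical PD". The text adds that early clinical progressors count even without imaging. "The primary efficacy analysis is conducted in the PPS".
- **FAS:** at least one dose and "at least one efficacy assessment of disease with either imaging studies or clinical examination after receiving study medication". Efficacy in the FAS is also reported.

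On replacement, section 5.4 says that patients "who withdraw in Cycle 1 for reasons unrelated to drug toxicity or PD will be replaced", and section 2.6.6 that those "who withdraw before completing Cycle 1 for reasons unrelated to drug AEs or PD will be replaced". Toxicity stops are therefore not replaced. Neither section mentions death.

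Table 1 and section 2.6.9 foresee permanent stops for toxicity. On timing, section 2.6.3 states: "Assessment of tumor response will be scheduled by end of the eighth week, then every 8 weeks". It also allows an earlier assessment if unacceptable toxicity occurs. Section 2.6.4 sets an end-of-treatment (EoT) visit for patients "discontinuing treatment for any reason except death will be assessed 30" (± 3) days after the last dose, or sooner if other therapy begins. A tumor assessment is due at that visit if the last one is more than 30 days old, and for patients without recorded PD "further tumor assessments are to be performed approximately every 3 months".

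Section 5.9 gives the ORR with an exact 95% CI and names no all-treated set for it. Its reference to the whole study population concerns PFS, DOR and OS only. The all-treated set in section 5.5.1 serves safety and treatment administration.

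**The concern.** The PPS keeps early failures due to progression in the denominator but not early failures due to toxicity or unexplained early death. The replacement rule keeps toxicity stops as patients who count towards the trial, yet the primary set then has no place for them. If they respond less often than the patients who stay in, the primary ORR is too high as a description of what happens to an eligible patient who starts the drug.

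Section 5.1 calls the study pivotal for approval in two countries. It has one arm, so the ORR carries the efficacy claim. The disposition table in section 5.5.4 will count patients dosed, evaluable and withdrawn for an adverse event. It does not split these by Cycle 1 or by reason for leaving the PPS, and it does not give the ORR with these patients included.

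**Working it through.** **Who is in which set** (eligible, dosed, PTCL confirmed):

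| Patient | PPS | FAS |
|---|---|---|
| Completes Cycle 1 | in | in, if assessed for efficacy at any time after the first dose |
| Stops in Cycle 1, clinical PD | in | in, if assessed after the first dose |
| Stops in Cycle 1, drug toxicity | out | in, if assessed after the first dose (usual, given the EoT visit) |
| Dies in Cycle 1, no recorded clinical-PD stop | out | in only if assessed before death |

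Completion of Cycle 1 is not defined by a number of doses, so a patient held for toxicity in Cycle 1 who stops later could be classed either way.

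**The plan's own figure.** Inputs from section 5.2: n = 40, reference rate 10%, target rate 30%, 5% two-sided alpha. No decision rule is written, so I take it as an exact lower 95% limit above 10%.

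- P(X ≥ 8 | 40, 0.10) = 0.0419, above 0.025
- P(X ≥ 9 | 40, 0.10) = 0.0155, below 0.025, so the critical value is 9
- P(X ≥ 9 | 40, 0.30) = 0.889

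This reproduces the stated 89%.

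**Effect on the estimate.** The documents give no count of omitted patients, so k = 2 to 6 is assumed. If they respond at rate q, ORR = (12 + kq)/(40 + k):

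| k | q = 0 (exact 95% CI) | q = 10% (expected) |
|---|---|---|
| 0 | 12/40 = 30.0% (16.6–46.5) | – |
| 2 | 12/42 = 28.6% (15.7–44.6) | 12.2/42 = 29.0% |
| 4 | 12/44 = 27.3% (15.0–42.8) | 12.4/44 = 28.2% |
| 6 | 12/46 = 26.1% (14.3–41.1) | 12.6/46 = 27.4% |

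A fall is not guaranteed: if one of three omitted patients responds, 13/43 = 30.2%.

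**Reading against 10%, added patients all non-responders.** Exact lower limits:

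- 9/40: 10.84%; 9/43: 10.04%; 9/44: 9.80%
- 10/50: 10.03%

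Adding up to 3 changes no reading. Adding 4 to 10 changes only a result of exactly 9/40. The chance of exactly 9/40 is 8.5% at a true PPS rate of 30% and 14.0% at 25%.

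**False-positive side.** Suppose the true ORR in all eligible treated patients is 10% and the k omitted patients are all non-responders. The PPS rate is then 0.10 × (40 + k)/40 = 10.5%, 11.0% or 11.5% for k = 2, 4 or 6. P(X ≥ 9 | 40) becomes 2.1%, 2.7% or 3.5%, against 1.5% with none omitted and a nominal one-sided 2.5%.

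**The case against.** The other side has four arguments.

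1. **Toxicity stops leave treatment, not assessment.** Section 2.6.3 allows an early scan when toxicity occurs. The last scan of a Cycle 1 stopper is normally the screening scan, so an EoT scan will usually be due. With a last dose around day 25, EoT falls near day 55 (25 + 30), about the time of the first scheduled scan. This stands: a lower response rate in toxicity stops is plausible but assumed. For Cycle 1 deaths it does not help.

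2. **The FAS already covers the gap.** It largely does, through the EoT visit or a clinical examination. What it still misses is treated patients with no post-dose efficacy assessment, chiefly early deaths and losses. A reader might infer that the FAS is no check at all because the two sets are not nested. The documents do not support that. The FAS needs an assessment after the first dose, not after Cycle 1, so only a patient with no efficacy assessment at all since starting could be in the PPS and outside the FAS. That should be rare.

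3. **Few patients may be affected.** Table 1 allows up to two weeks for recovery before most toxicity stops, so such a stop within 28 days needs onset in roughly the first 14. This stands, and the count is unknown.

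4. **The SAP may contain the missing analysis.** Section 5.1 defers detail to it, and its text is not shown. The finding is therefore limited to the documents provided. The PPS definition and its primary status are, however, already set in the protocol.

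**Conclusion.** The gap in the primary set is clear from the wording. An upward bias is likely, but its direction rests on the omitted patients responding less often than the PPS, and its size on an assumed 2 to 6 patients. In that range the ORR falls from 30.0% to between 28.6% and 26.1% if none of them responds, and to between 29.0% and 27.4% if they respond at 10%. If no such patient occurs, the effect is zero.

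A reader might go further and infer that the bias is certain, or that the efficacy conclusion is unsafe. Neither follows. A toxicity stop can have a documented response. No pass/fail rule is written, section 5.1 calls the analysis primarily descriptive, and 10% appears only in the power statement. Even read as a threshold, it is affected only at 9/40 for 4 to 10 added non-responders.

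Severity is minor to moderate. Confidence is high on the wording and moderate on the direction and size of the bias.

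**What to change.** Remove the post-dose-assessment condition from the FAS, so that it holds all eligible patients with at least one dose who were not judged non-PTCL on central pathology review. If the FAS wording is already fixed, add this as a separate all-treated set. Count patients with no post-dose efficacy assessment as non-responders. Report this ORR with its exact 95% CI as a named sensitivity analysis beside the PPS. Tabulate exclusions from the PPS by reason: Cycle 1 toxicity, Cycle 1 death, withdrawal, loss to follow-up.

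Extend the PPS itself to Cycle 1 toxicity stops and deaths only if this can be done without knowledge of the data. Version 6.0 is dated July 2021 and last patient in was planned for 3Q 2018, so that may no longer be possible.

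The cost is wording and one table on data already collected, with no new patients or visits. The reported ORR may be slightly lower, and the set is conservative because it also takes in dosed patients who were replaced under section 5.4. If the PPS rate is 30% and 4 non-responders are added, 10/44 is needed to clear 10%, and the chance of doing so is P(X ≥ 10 | 40, 0.30) = 80.4%, against 88.9% for the PPS alone. As a sensitivity analysis this leaves the power of the primary analysis unchanged.

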5.5.3 Pharmacokinetic Population

All patients who have pretreatment baseline and at least 1 blood sample on study providing PK data for HBI-8000.

5.5.4 Patient Disposition

Data tabulations will summarize the following patient numbers:

- Enrolled
- HBI-8000 treatment dose received
- Evaluable for safety and efficacy
- Protocol violations
- Protocol completions
- Withdraw from study due to:
 - Adverse event
 - Physician's recommendation
 - Withdraw consent
 - Lost to Follow-up
 - Other reasons as collected on the eCRF

5.6 Patient Characteristics

Demographic and baseline characteristics of patients will be summarized using descriptive statistics:

- Age
- Gender
- Race
- Ethnicity
- ECOG Performance Status
- Prior therapies
- Other baseline characteristics as collected on the eCRF

5.7 Concomitant Medications

The number and proportion of patients using different concomitant medications will be tabulated and summarized by WHO Drug anatomical therapeutic chemical (ATC) classification system and preferred term.

5.8 Treatment Administration

Study drug administration will be described in terms of the total number of cycles administered, the median (range) of cycles administered, dose intensity, and reasons for the deviations from planned therapy.

5.9 Efficacy Analysis

The efficacy endpoints are the following:

Primary Endpoint:

- ORR(CR + PR)

Secondary Endpoint:

- ORR by disease subtype (see Section 2.5.1)
- Median duration of PFS
- Median DOR

Exploratory Endpoint

- Median duration of OS

Response rate endpoints (ORR and ORR by disease subtype) will be summarized by number and percentage of patients meeting the definition of ORR along with the corresponding exact 95% CI. Tumor response as assessed by imaging studies will be adjudicated by independent radiology reviewers. Tumor lesions, such as skin lesion, that cannot be monitored by imaging studies will be determined by independent oncology reviewers and contributed to overall disease response assessment. Both investigators reported and independently adjudicated outcomes will be reported. Primary analysis will be based on results from imaging studies and clinical data confirmed by Independent Central Review. Results from investigator assessment will also be reported. In addition, the ORR will be analyzed according to histology subtypes of PTCL. The subtypes reported by Central pathology review for each patient will be used for such analysis.

Time-to event endpoints (PFS, DOR, and OS) for entire study population will be summarized by Kaplan-Meier methods (median, 95% CI, number of events, number censored and Kaplan-Meier figures).

5.10 Safety Analysis

All patients who receive one dose (any amount) of HBI-8000 will be included in the summaries and listings of safety data. Overall safety profile and tolerability will be characterized by type, frequency, severity, timing, duration, and relationship of study therapy of AEs and laboratory abnormalities.

5.10.1 Adverse Events

Adverse events will be classified using the MedDRA classification system version 19.0 or higher. The severity of the toxicities will be graded according to the NCI CTCAE version 4.03.

In all summaries, emphasis will be placed on treatment emergent adverse events (TEAEs), namely, those with initial onset or that worsen in severity after the first dose of HBI-8000. TEAEs will be summarized by the frequency of patients experiencing TEAEs corresponding to body systems and MedDRA preferred term and by worst NCI CTCAE (version 4.03) grade. Summaries will also be provided of treatment related TEAEs, namely, those judged by the investigator to be related or likely related to HBI-8000.

TEAEs resulting in discontinuation of HBI-8000 treatment or withdrawal from the study, Grade 3 or higher, SAEs, and deaths on-study will be tabulated.

5.10.2 Laboratory Tests

Laboratory data will be summarized for the observed values at each scheduled assessment, together with the corresponding changes from baseline (the value obtained prior to dosing on Day 1 of Cycle 1) using descriptive statistics.

For those analyses with CTCAE grades, abnormal laboratory values will be summarized by shift tables displaying numerical values and percentages classified by Baseline grade (e.g., grade prior to dosing on Day 1 of Cycle 1) and maximum grade on treatment. All laboratory data will be presented in listings.

5.10.3 ECGs

Serial ECGs will be performed to evaluate the potential effects of the study drug on the heart. The ECG parameters (PR interval, QRS duration, QT, QTc and QTcF) will be summarized descriptively for each time point for both the observed values and the change from Baseline to each post-baseline time point. The number and percentage of patients with QT or QTc (QTcF) outlier values (at any post-baseline time point), as defined in ICH E14, will be summarized.

5.10.4 Vital Signs and Physical Findings

Vital signs data will be summarized by the observed values at each scheduled assessment, together with the corresponding changes from Baseline using descriptive statistics.

Physical findings will be presented in data listings.

5.10.5 Interim Analysis

No interim analysis for efficacy is planned for this Phase 2b study.

5.11 Pharmacokinetic Analysis

In patients participating in PK study, peripheral blood will be sampled at specified time points. Plasma concentration of HBI-8000 will be listed and summarized using descriptive statistics. PK data collected in this study will be combined with PK data collected from other studies and a population PK analysis will be performed. Results of the population PK analysis will be presented in a report separate from the CSR.

6.0 ETHICS

6.1 Institutional Review Board or Independent Ethics Committee

The protocol, ICF and any other written information and/or materials to be provided to the patients and the amendments (as required by local regulations) should be reviewed and approved by the IRB/Independent Ethics Committee (IEC). The sponsor's authorized representative should be provided with documentation of IRB/IEC approval of the protocol and informed consent before the study may begin at the study center(s).

The only circumstance in which an amendment may be initiated prior to the sponsor and IRB/IEC approval is where the change is necessary to ensure the safety of the patients. In that case, the investigator must document the change and notify the sponsor and IRB/IEC in writing immediately after the implementation.

The investigator should submit written summaries of the study status for review by the IRB/IEC annually, or more frequently if requested by the IRB/IEC. Upon completion of the study, the investigator will provide a brief report of the outcome of the study, if required. The sponsor and/or the sponsor's authorized representative will handle the distribution of any of these documents to the national regulatory authorities.

